8.0 Research Setting

8.1 Describe all facilities/sites/locations where you will be screening and conducting research procedures.

Example: "A classroom setting in the Department of Psychology equipped with a computer with relevant survey administration software," "The angiogram suite at Stony Brook University Hospital, a fully accredited tertiary care institution within New York State with badge access," etc.

Response: Jefferson's Ferry Independent Living at the Wellness Center/gym or other area as designated by Jefferson's Ferry

8.2 For research procedures being conducted internationally), Supplemental Form C must be completed and uploaded.

Response:

- ⋈ N/A: This study is not conducted outside of SBU or its affiliates.
- 8.3 For research procedures conducted externally to Stony Brook University (e.g. other institutions, schools, other states), attach applicable approval letter(s) in the myResearch IRB smartform.

Response: Please see attached approval letter from Jefferson's Ferry.

9.0 Resources and Qualifications

9.1 The Principal Investigator (PI) must confirm, in consultation with Chair and Dean as applicable, that adequate resources are present to conduct and complete the study compliantly and safely. Specifically:

Protocol Title (Running Head):		
□ NO ☑YES The proposed subject population(s) are available in sufficient numbers to meet the study requirements.		
□ NO ☑YES Sufficient funds are available to conduct and complete the study compliantly and safely.		
□ NO ☑YES The PI and study team have sufficient time to conduct and complete the study compliantly and safely.		
□ NO ☑YES The PI has determined that the named study team is qualified to conduct the research compliantly and to monitor the safety and welfare of the enrolled research subjects effectively.		
□ NO ☑YES The PI ensures that the study team is fully aware of his/her involvement n this study and the details of the study protocol.		
□ NO □ YES The PI ensures that the study teams will only be involved in research procedures for which they have been trained, and are currently certified and/or licensed, if equired.		
□ NO		
Response:		
10.0 Other Approvals		
10.1 List approvals that will be obtained prior to commencing the research (e.g., University Hospital signoffs per the UH Application, Cancer Center Scientific review, external site, funding agency, laboratory, Radiation Safety, IBC, SCRO, IACUC, RDRC).		
Response:		

11.0 Provisions to Protect the Privacy Interests of Subjects

⊠ N/A: This study does not require any other approval.

11.1 Describe how you will protect subjects' privacy interests during the course of this research.

NOTE: Privacy refers to an individual's desire/right to control access to or to place limits on whom they interact with or whom they provide personal information. Privacy applies to the person. Examples of appropriate responses include: "participant only meets with a study coordinator in a private office setting where no one can overhear", or "the participant is reminded that they are free to refuse to answer any questions that they do not feel comfortable answering."

Response: The participant is reminded that they are free to refuse to answer any questions that they do not feel comfortable answering. Participants will only meet with a study coordinator in a private consultation room at Jefferson's Ferry.

12.0 Confidentiality

A. Confidentiality/Security of Study Data

Describe the local procedures for maintenance of security and confidentiality of study data and any records that will be reviewed for data collection.

NOTE: Confidentiality refers to how data collected about individuals for the research will be protected by the researcher from release. Confidentiality applies to the data.

12.1 Where and how will all data and records be stored? Include information about locked cabinet/locked office, authorization of access, certificates of confidentiality, and separation of identifiers and data, as applicable. Include physical (e.g., paper) and electronic files (e.g., storage of data in REDCap) password protection, encryption.

Response: All data and records will be stored locally on secure Stony Brook Medicine networks. The only identifying data is the consent form. However, this will not be linked to the unique random study code/participant id number. The data will be collected during study visits and deidentified, with participant identifiers being replaced by unique study codes. The de-identified data will be encrypted and securely stored on Stony Brook Medicine encrypted servers, which meet institutional security standards. Access to the data will be restricted to authorized personnel, with password-protected systems and encryption in place to ensure data security. Additionally, all identifiable information, such as consent forms will be uploaded to a secure

Stony Brook Medicine shared drive and then disposed in the secure Health Sciences Center (HSC) discard bin.

The optional Onform app video recordings will be stored on the apps HIPPA compliant platform. The face will be obscured.

The physical forms (i.e. pre and post questionnaires, performance on the app, CDC tests, device sensory thresholds) will be transported to SBUH by research personnel and will be stored separately in a secured, locked file cabinet until they can be uploaded (scanned) into the secured shared drive, at which point all physical forms will be discarded in the Stony Brook Medicine HSC secure bins. Answers to the study questionnaires, performance on the 3 CDC tests as well as gait analysis app findings, Accelera device sensory thresholds, will also be entered into an excel sheet on the Stony Brook Medicine shared drive.

12.2 Who will have access to the data?

Response: Access to the data will be restricted to the Principal Investigator and the designated research staff involved in the study, including research assistants, data managers, and statisticians. Accelera company will only have access to the aggregate data from the study.

NOTE: If there are plans to share datasets with unrestricted access, adjust language in the consent form to reflect this. Consider including the phrase: "Your data and biospecimens will be shared in a way where anybody around the world can gain access to them without review."

12.3 How will the data be transported/transmitted (if applicable)?

Response: Data will be transported and transmitted securely using password-protected, encrypted spreadsheets. De-identified electronic files will be stored on Stony Brook Medicine networks. For data sharing with collaborators, including the study sponsor Accelera, deidentified data will be transmitted via encrypted emails.

Videos/data collected via the Onform app platform is maintained on the apps' HIPAA compliant platform.

12.4 Describe if identifiers will be retained, de-identification of the data is not feasible, or whether there are circumstances in which re-identification may be possible.

Response: De-identified data will be stored separately from any identifying information, which will be encrypted and stored in a separate, secure file to ensure confidentiality. Participants'

faces will be obscured in the video recordings on the Onform app. Only authorized study personnel will have access to the data.

If this study includes data collected from individuals, groups, or populations with unique attributes (e.g., Tribal Nations, international sites) that may increase the risk of re-identification, describe how sensitive information regarding potentially stigmatizing traits, illegal behaviors, or other information that could be perceived as causing group harm or used for discriminatory purposes will be protected.

				1 _
Res	וטטו	ise:	11/	a

12.6 Describe circumstances under which a code key may be used to re-link identifying information to data/specimens?

Response: n/a

B. Confidentiality of Study Specimens

Describe the local procedures for maintenance of confidentiality of study specimens.

N/A: No specimens will be collected or analyzed in this research.

Where and how will all specimens be stored? Include information about: locked freezers, locked laboratories, authorization of access, and labeling of specimens, as applicable.

Response: n/a

12.8 Are there limits for the future use of biospecimens in any way? Such as controlled access to the data based on laws, regulations, policies, and agreements.

Response: n/a

12.9 Who is responsible for receipt or transmission of the specimens (if applicable)? If you are transporting specimens to another location not affiliated with Stony Brook University, you must have a Material Transfer Agreement.

Response: n/a

12.10 Banking Data or Specimens for Future Unspecified Use

N/A: This study is not storing data or specimens for research outside the scope of the present protocol. This section does not apply.

NOTE: If you are proposing to bank specimens for future use, you may be subject to licensure requirements under the NYS Department of Health and must be covered under the SBU license. See SOPs section 17.2 at https://www.stonybrook.edu/research-compliance/Human-Subjects/sops.

12.11 If data will be banked for research outside of the scope of the present protocol, describe where the data will be stored, how long they will be stored, and who will have access to the data.

NOTE: Your response here must be consistent with the information provided to subjects in your Consent Documents

Response:

12.12 Will specimens be obtained from specific cultural groups? Consider whether your study will include specimens collected from individuals, groups or populations with unique attributes (e.g., Tribal Nations, international groups) that may increase the risk of re-identification. Describe how sensitive information regarding potentially stigmatizing traits, illegal behaviors, or other information that could be perceived as causing group harm or used for discriminatory purposes will be protected.

Also, consider cultural sensitivities around the return and/or destruction of biospecimens when research participants withdraw their consent for the storage and sharing of data and biospecimens or when data and biospecimens need to be maintained.

Protocol Title (Running Head):			
NOTE:			
In general, participants should be given the choice about whether or not they wish to have their data and biospecimens stored and shared for future use. Providing options for participants to agree to data and biospecimen storage and sharing is particularly important in studies that offer the prospect of direct benefit to the participant. Requiring storage and sharing may be considered undue influence if the participant does not want to agree to sharing of data and biospecimens but feels compelled to agree anyway to join a possibly beneficial research study.			
If the primary research study offers no prospect of direct benefit, it may be reasonable to consider requiring storage and sharing in the primary protocol (e.g., if the primary protocol is a repository protocol with the sole purpose being to collect data and/or biospecimens for future use). In this case, there is no reason to participate if the participant does not want to provide consent for storage and sharing.			
NIH Funded Research: Upload a copy of the Data Management and Sharing Plan			
Response:			
13.0 Withdrawal of Subjects			
□ N/A: This study is not enrolling subjects. This section does not apply.			
13.1 Describe anticipated circumstances under which subjects may be withdrawn from the research without their consent.			
Response: if the participant is unable to participate in the study during the study session for any reason, including inability to walk, they would be withdrawn from the study			

13.2 Describe any procedures for orderly termination.

NOTE: Examples may include return of study drug, exit interview with clinician. Include whether additional follow up is recommended for safety reasons for physical or emotional health.

Response: n/a

13.3 Describe procedures that will be followed when subjects withdraw from the research, including retention of already collected data, and partial withdrawal from procedures with continued data collection, as applicable.

Response: If a subject withdraws on the day of the study before information is deidentified, their data will be removed. This includes removal of data/videos from the Onform app if they had opted in to participate.

13.4 Describe what will happen to data already collected.

Response: Data can only be discarded at the time of the study session if the participant requests. After that, we would not be able discard it as there is no matching between the person who signed the consent and the random participant/subject ID. As we are not keeping any picture of the participants and faces will be obscured on the Onform video recording, after the session, we would not be able to delete the videos.

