assistance devices, if any. In other words, a video recording is made with the app and stored on the apps' HIPAA compliant platform. With the faces obscured, measurements of their gait/mobility will be performed using additional programs as indicated in the Data section. After bracelet application, volunteers will then be encouraged to resume their normal ambulation-(while using their usual mobility assistive devices) for about 30 minutes at the study location as described below. The same 3 tests will be repeated after 30 minutes, along with a post-study questionnaire, and if they consented to video recording above, then repeat videorecording with the Onform video recording app would be performed. With the faces obscured, measurements of their gait/mobility will be performed using additional programs as indicated in the Data section. At this point, the ankle bracelets will be removed – with the subjects having worn them for about 1 hour total. There will be an additional up to 1 hour for completion of the pre- and post-study questionnaires, for a total study session duration of about 1.5 - 2 hours. At each session, we will apply these bracelets to a minimum of 1 patient per session. These sessions will occur at the Wellness Center/gym or other designated area at Jefferson's Ferry 1x per week, with a minimum of one patient for up to 8 patients/week if no holidays, until 20 patients have completed the study. To address infection control, a disposable sock will provide a physical barrier between the device and patient, while still allowing the patient to feel the stochastic resonance.

3.2 Include the number of subjects and the power analysis. If applicable, indicate your screen failure rate, i.e., how many subjects you expect to screen to reach your target sample.

Response: 20 volunteers will be enrolled. The study would continue until 20 volunteers are enrolled and complete all non-optional parts of the single study session.

3.3 Indicate the duration of the subject participation including long-term follow-up.

Response: A single study session. There is no long-term follow-up in this study.

3.4 Indicate whether you are specifically recruiting or targeting any of the following special populations in your study using the checkboxes below.

Response: n/a

Minors (under 18 years old)

Adults unable to consent

Pregnant women

Protoco	ol Title (Running Head):
	Prisoners

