There will generally be 1 session per week at Jefferson's Ferry, at the Wellness Center/gym or other designated area at Jefferson's Ferry, with a minimum of one patient for up to 8 patients/week if no holidays, until 20 patients have completed the study. It is currently tentatively planned for Mondays, excluding holidays and other institutional/researcher availability requirements. However, this may be adjusted in coordination with Jefferson's Ferry.

Possible participants will be able to sign up at the educational session for additional information. Additionally, they will be advised that they can come sign up at any date that we are having a study session. They would only complete the screening/survey questionnaires at a study session.

If the participants opt in, then the app that will be used for mobility analysis during the study is called Onform, from Onform Inc. It is a HIPAA compliant video recording and analysis App. The video recording that is saved will be saved as per the app specifications using a first and last name, however the first name will be the 1st digit of the subject ID code, and the last name will be the last digit of the subject ID code. As indicated above, participants' faces will be obscured. Analysis will be as described in section 3.7 above. Please see the attached app privacy policy.

7.2 Describe what data, including long-term follow-up data, will be collected.

NOTE: For studies with multiple data collection points or long-term follow-up, consider the addition of a schedule or table in your response.

Response: The data being analyzed includes participant pre and post study questionnaires, including demographics, sensory thresholds for the Accelera device, 30-second chair stand, 4 stage balance test, and timed up and go (TUG) task outcomes. There will also be mobility/gait/posture analysis performed via an iPad/iPhone App without the participant's name before and while wearing the ankle bracelets. Researchers will provide basic prompts regarding participants' stability and gait. Participants will also complete a self-reported health/exercise/fear of falling questionnaire at the start of the visit and at the end of the visit as well as a post questionnaire. We will also evaluate for falls with or without the device at the study session. There is no long-term follow-up.

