Response: This study will be performed in a fixed location at Jefferson's Ferry, e.g. wellness center/gym. Participants will remain at this location for the duration of the study and hence will be in a controlled setting for monitoring.

14.8 Provide information about the Data and Safety Monitoring Plan.

Response: This is a pilot study on an FDA exempt class I device that is available over the counter. We will actively monitor and record any falls or other device-related adverse events occurring during study participation. Although the study poses minimal risk, we recognize the importance of safety monitoring. An independent monitor, [name], not part of the research team, will be designated to oversee the safety data, specifically the fall incidence. This individual will receive fall data at regular intervals (e.g. each time 5 participants have completed the study – so they would receive data a total of 4 times, as this would indicate all 20 participants have completed the study) and will recommend pausing or terminating the study if an excessive fall rate is observed or if participant safety is otherwise compromised.

14.9 Provide information if a medical monitor will be used to monitor the safety of the study.

14.10 Provide information if a Data and Safety Monitoring Committee/Board will be used to monitor the safety of a study that is greater than minimal risk. Provide justification if a Data and Safety Monitoring Committee/Board will not be used.

☑ N/A:

Response:

14.11 Describe what data are reviewed, including safety data, and efficacy data.

Response:

Response: no

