In addition, all participant information collected during the screening process will be de-identified and stored securely. The research team will use a unique identifier for each participant, and all identifiable information (e.g. consents) will be kept in locked cabinets, until they are uploaded into a secured Stony Brook Medicine shared drive accessible only to designated research personnel. Furthermore, electronic information will be stored on password-protected, encrypted servers to prevent unauthorized access.

18.4 Describe how you will ensure that subjects are provided with sufficient time to consider taking part in the research study. Detail if there is any time period expected between informing the prospective subject and obtaining the consent.

NOTE: It is required that the prospective subject receive sufficient time to have their questions answered and to consider their participation

Response: The study has been approved by Jefferson's Ferry leadership. Prior to initiation of the study, there will be an 'open house' type forum(s) at Jefferson's Ferry, where we will discuss the study. As this is purely voluntary, only interested participants are expected to enroll.

18.5 Describe the process to ensure the subject's ongoing willingness to continue participation for the duration of the research study.

Response: There is only a single study session in the study. The participant may withdraw at any time during the single study session.

Non-English Speaking Subjects

- ⋈ N/A: This study will not enroll Non-English speaking subjects.
- 18.6 Indicate which language(s) other than English are likely to be spoken/understood by your prospective study population or their legally authorized representatives.

Response:

18.7 If subjects who do not speak English will be enrolled, describe the process to consent the subjects, as well as the process to be used to ensure their understanding of research procedures throughout the conduct of the study. Review SOPs section 17.8 for important policies in this regard: https://www.stonybrook.edu/research-compliance/Human-Subjects/sops).

Response:

Adults Unable to Consent

- N/A: This study will not enroll adults unable to consent.
- 18.8 Justify why it is necessary to include adult subjects who are unable to consent.

Response:

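### Sections 13.3 and 13.4 give different rules for removing a withdrawer's data, and neither exempts the falls and adverse events that 14.8 says will be recorded

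*Protocol*

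**What the plan says.** All references are to the protocol.

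- **13.3**, on withdrawal: "If a subject withdraws on the day of the study before information is deidentified, their data will be removed". Videos and data in the recording app are included. No request is needed, and nothing is carved out.
- **13.4**, on data already collected: "Data can only be discarded at the time of the study session if the participant requests". The reason given is that after the session nothing connects a consent to a study ID.
- **13.1**: anyone unable to take part for any reason, "including inability to walk, they would be withdrawn from the study". It does not say whether the removal rule in 13.3 applies to them.
- **18.5**: "The participant may withdraw at any time during the single study session".
- **7.2**, on data collected: "We will also evaluate for falls with or without the device at the study session".
- **14.8**: "We will actively monitor and record any falls or other device-related adverse events occurring during study participation". An independent monitor receives fall data at intervals, for example "each time 5 participants have completed the study", four times in all. The monitor can recommend a pause or termination if the fall rate is excessive or safety is otherwise compromised.
- **3.2**: "The study would continue until 20 volunteers are enrolled and complete all non-optional parts of the single study session".

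**The concern.** The events that matter most to a fall monitor are those that make a person stop. Section 14.2 itself foresees dizziness, imbalance and falls, and 13.1 foresees people who cannot walk. If stopping can lead to deletion of everything collected, including the record of the fall, the safety description is thinned in one direction, in favour of the device.

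The design does not correct for this. A person who stops is in effect replaced, because enrolment runs to 20 completers. With no link between person and ID, no access to medical records (7.4) and no follow-up (3.3), a deleted event could not be reconstructed.

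What is at stake is the fall and adverse-event account of a 20-person pilot and the information its monitor acts on. People who get worse but finish the session stay in the data.

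**Working it through.** **1. The plan's own figure.** One report per 5 completers, 20 completers: 20 / 5 = 4 reports, as 14.8 states.

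**2. The two removal rules side by side.**

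| | 13.3 | 13.4 |
|---|---|---|
| Trigger | withdrawal itself | participant's request |
| Window | study day, before de-identification | at the study session |
| Exception for falls or adverse events | none | none |

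The protocol does not fix the moment of de-identification. Sections 3.7 and 12.1 suggest data are coded from collection or soon after, yet 13.3 expects app videos still to be removable, so the window is neither empty nor defined.

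**3. How often the rules come into play.** There is one session and no follow-up, so every voluntary withdrawal falls on the study day. The first condition of 13.3 is then always met; the second, before de-identification, may or may not be.

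**4. Whether falls are within the data to be removed.** Section 7.2 lists falls at the session among the data collected, so a participant's data includes them on its plain meaning. Section 14.8 requires falls to be recorded but does not say that the record survives removal, and 14.11 to 14.14 add nothing on this.

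**5. Effect on the rate (illustration only).** Let f be falls among the 20 completers and w the fallers who stopped, were removed and were replaced. Both are assumptions.

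- Recorded rate = f / 20.
- Rate with removed fallers restored = (f + w) / (20 + w).

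Exact (Clopper-Pearson) 95% limits: for x = 0, the upper limit is 1 − 0.025^(1/n). For x ≥ 1, the lower limit is the 0.025 quantile of Beta(x, n − x + 1) and the upper is the 0.975 quantile of Beta(x + 1, n − x).

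| Assumption | Recorded | Restored |
|---|---|---|
| f = 0, w = 1 | 0/20 = 0% (0 to 16.8%) | 1/21 = 4.8% (0.1 to 23.8%) |
| f = 0, w = 2 | 0/20 = 0% (0 to 16.8%) | 2/22 = 9.1% (1.1 to 29.2%) |
| f = 1, w = 1 | 1/20 = 5.0% | 2/21 = 9.5% |
| first report, f = 0, w = 1 | 0/5 = 0% (0 to 52.2%) | 1/6 = 16.7% (0.4 to 64.1%) |

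**6. Likelihood.** With p the chance of a fall in a session and q the chance that a faller stops and is removed, the chance of at least one removal among 20 starters is 1 − (1 − pq)^20. The protocol gives neither p nor q. Its only fall frequency, about one in four people over 65 per year (2.1), is an annual figure for a general population. Over assumed ranges of p from 1% to 10% and q from 25% to 100%, the result runs from 1 − 0.9975^20 = 4.9% to 1 − 0.90^20 = 87.8%. So wide a range supports no statement about probability.

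**The case against.** The strongest case for the plan is that 13.3 and 13.4 answer overlapping form questions and can be read together, with 13.4 as the limit on 13.3. Loss would then need a faller who stops and also asks for deletion during the session. Section 14.8 is the specific safety provision, covers any fall during participation and makes no exception for withdrawers, so it can be read as standing beside 13.3. Sessions are monitored, falls are not a stated objective, no numeric fall threshold exists for a lost record to cross, and the intervals above overlap almost wholly.

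Much of this limits the size of the point but does not remove it. The joint reading may settle the window; it does not settle whether removal is automatic or on request, and no sentence says which rule governs or that safety records are untouched.

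A reader might infer more than the text supports:

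- *That 14.8 promises to keep fall records.* It promises to monitor and record them; keeping is only implied by their use in a rate.
- *That 13.3 deletes the data of every voluntary withdrawer.* It applies only before de-identification.
- *That the monitor sees completers only.* Completion sets the timing of reports, given as an example; the content is not restricted to completers.
- *That stored consents would reveal a missing person.* The protocol does not say that a withdrawer's consent is kept.

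**Conclusion.** The point holds as a contradiction in trigger and window between 13.3 and 13.4, together with a missing exemption for the events that 14.8 says will be recorded. Following 13.3 as written can take a faller who stops out of both numerator and denominator of the rate the monitor judges.

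The loss is possible, not certain, and the protocol gives no basis for saying how likely. If one faller were removed and no completer fell, 1/21 would be reported as 0/20, a difference of 4.8 percentage points; at a first report it would be 1/6 against 0/5. These figures rest on assumed counts and show scale only. The effect is on the safety description. It should be settled before sessions begin, because a deleted record cannot be recovered.

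**What to change.** - **13.3 and 13.4:** state one rule. Data already collected are kept under the study ID unless the participant asks for removal before the session ends.
- **Same place:** state that fall and adverse-event records are kept, under the study ID only, for everyone who starts the session, before or after the bracelets are fitted, including those withdrawn under 13.1. Limiting this to people already fitted would miss falls during the baseline tests, although 7.2 counts falls with and without the device.
- **14.8:** keep the reporting times. State that the fall data sent to the monitor cover everyone who has started a session to date. Report falls with that denominator, giving falls before and while wearing the device separately.
- **Consent form:** make it say the same. Its pages were not available for this review, so it may already do so.

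The target of 20 completers in 3.2 can stay. The cost is a few sentences, with no extra participants, procedures or monitor reports. Participants lose the option of having a fall or adverse-event record deleted and must be told so, and the safety rates may look slightly less favourable. Repeat-test results for people who stop early remain missing.
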